**Table 2: PLX3397 Dosing Cohorts**

Cohort	Combination PLX3397/RT/TMZ		Adjuvant PLX3397/TMZ	
	PLX3397 Dose	PLX3397 Schedule	PLX3397 Dose	PLX3397 Schedule
-2	600 mg/day	5 days/week (M-F) b	800 mg/day b	7 days/week
-1	600 mg/day	7 days/week a	600 mg/day a 800 mg/day b	7 days/week
1	800 mg/day	7 days/week a 5 days/week (M-F) b	1000 mg/day b	7 days/week
2	1000 mg/day	5 days/week (M-F) b	1200 mg/day b	7 days/week

a Amendment 1.

b Amendment 2.

Study drug will be administered orally using a capsule formulation (200 mg per capsule). The total daily dose of PLX3397 will be divided and administered BID. For an uneven number of capsules, the larger dose will be administered in the morning.

For combination PLX3397/RT/TMZ PLX3397 treatment, dose escalation to the next highest cohort may occur after all patients have completed the 11-week DLT-observation period (i.e., 1-week PLX3397 monotherapy; 6-week PLX3397/RT/TMZ combination therapy; 4-week recovery). For adjuvant PLX3397/TMZ PLX3397 treatment, dose escalation to the next highest cohort may occur after all patients have completed an 8-week DLT-observation period (i.e.,

2 cycles of adjuvant treatment). For patients participating in Phase 1b, intra and inter patient dose escalation to a higher dose level/schedule will be permitted after that dose level/schedule has been established to be safe.

Prior to dose escalation, safety data will be collated and reviewed by the Sponsor and study sites by teleconference. A dose level will be considered unacceptable if 2 or more patients of the 6 eligible patients experience a DLT (see below). Should all 7 patients in the Cohort be analyzable for adverse events, only the first 6 will be considered in the determination of DLTs. A patient who misses more than 7 days of PLX3397 administration during the 7-week dosing period of Cycle 1 (4 weeks) and Cycle 2 (3 weeks) for reasons other than having had a DLT will be replaced. If 2 or more patients in a Cohort experience a DLT, no patients in the Cohort will be replaced.

If 2 or more of the first 6 patients in Cohort -2 (600 mg/day of PLX3397; 5 days/week [M-F]) experience a protocol-defined DLT, the combination will be considered too toxic and the study will be discontinued.

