### **13.16 Stopping Rules**

The Plexxikon Medical Monitor will monitor safety data throughout the course of the study. The Medical Monitor will review SAEs within timeframes mandated by company procedures and will review trends, laboratory analytes, and adverse events at periodic intervals and provide for interim safety analyses if appropriate. Safety data across all study patients will be reviewed at planned bimonthly teleconferences with all participating sites.

For Phase 1 dose escalation, a dose level will be considered unacceptable if 2 or more patients of the 6 eligible patients experience a DLT (see below). Should all 7 patients in the Cohort be analyzable for adverse events, only the first 6 will be considered in the determination of DLTs. A patient who misses more than 7 days of PLX3397 administration during the 7-week dosing period of Cycle 1 (4 weeks) and Cycle 2 (3 weeks) for reasons other than having had a DLT will be replaced. If 2 or more patients in a Cohort experience a DLT, no patients in the Cohort will be replaced.

If 2 or more of the first 6 patients in Cohort -2 (400 mg/day of PLX3397) experience a protocol-defined DLT, the combination will be considered too toxic and the study will be discontinued.

After approximately 50% of the planned Phase 2 patients have been completed their concurrent radiation therapy, an overall interim safety summary will be reviewed by the Medical Monitor and principal investigators to ensure that the potential clinical benefit outweighs the observed clinical risk to date. If the safety observations do not warrant continued enrollment, the study will be discontinued.

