## **21.0 STATISTICAL ANALYSIS**

### **21.1 General Statistical Considerations**

#### **21.1.1 Phase 1b Portion**

The objective of the Phase 1b portion of this study is to determine the recommended Phase 2 dose (RP2D) of PLX3397 when combined with concurrent radiation therapy and temozolomide. Two expected dose levels are specified for testing, with one or more lower doses to be evaluated if the starting dose of 800 mg/day is above the MTD. For each dose level, 7 patients will be accrued to assure that there will be 6 patients eligible for evaluation of toxicity. A patient registered to the study who is found retrospectively not to meet the study eligibility criteria, who does not receive any PLX3397, or who is considered non-evaluable during the toxicity evaluation period for reasons not related to study drug will be excluded from evaluation of DLT and replaced.

Patient accrual will be suspended after each dose cohort is enrolled until there is sufficient information collected to make a decision relative to dose escalation. A dose level for PLX3397 will be considered acceptable if no more than 2 patients of the 6 eligible patients experience a DLT. Should all 7 patients be analyzable for adverse events, only the first 6 will be considered in the determination of DLTs. If the current level is considered acceptable, then dose escalation will occur and the protocol will be reopened. Otherwise, the preceding acceptable dose level will be declared the MTD. The Sponsor, together with the study investigators, will evaluate the safety of each cohort prior to dose escalation.

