## **21.7 Pharmacodynamic Analysis**

### **21.7.1 Central histopathologic review and tissue requirements**

At least 20 unstained FFPE slides from a representative block of tumor tissue (0.5 cm diameter) should be submitted on all participants in the study. One slide will be H&E stained at the central site to confirm diagnosis and determine eligibility for further study. The remaining slides will be utilized for MGMT methylation assessment, biomarker analysis, and correlation of treatment effect with genotype and phenotype.

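### The dose-escalation count can leave out DLTs seen in dosed patients: a 7th evaluable patient, and anyone later found ineligible

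*Combined protocol and SAP*

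**What the plan says.** Section 21.1.1 sets the cohort size: "For each dose level, 7 patients will be accrued to assure that there will be 6 patients eligible for evaluation of toxicity". It then limits the count: "Should all 7 patients be analyzable for adverse events, only the first 6 will be considered in the determination of DLTs". Section 13.13.1 (text under Table 2) has nearly identical wording: "Should all 7 patients in the Cohort be analyzable for adverse events, only the first 6 will be considered in the determination of DLTs". Section 13.16 repeats that "only the first 6 will be considered in the determination of DLTs", as does the Stopping Rules row of the synopsis.

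Section 21.1.1 also lists patients who leave the DLT evaluation. One group is "A patient registered to the study who is found retrospectively not to meet the study eligibility criteria". Never having received PLX3397 is a separate item in the same list, as is being non-evaluable for reasons unrelated to study drug. All of them "will be excluded from evaluation of DLT and replaced".

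The missed-dose rule in Sections 13.13.1 and 13.16 and the synopsis works differently: a patient who misses more than 7 days is replaced only if the cause was something other than a DLT.

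The thresholds conflict. Section 21.1.1 reads: "A dose level for PLX3397 will be considered acceptable if no more than 2 patients of the 6 eligible patients experience a DLT". Sections 13.13.1 and 13.16 and the synopsis call a level unacceptable once 2 or more of the 6 have a DLT.

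**The concern.** The count decides whether a level is acceptable and so steers the choice of the recommended Phase 2 dose. Two clauses let a DLT in a treated patient drop out of it.

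- **The 7th patient.** Section 13.13.1 allows escalation on the combination regimen only after all patients have finished the 11-week window. The 7th patient's outcome is therefore known when the decision is made, and leaving it out saves no time.
- **Later ineligibility.** Failing an entry criterion does not undo a toxicity that occurred on the drug. The missed-dose rule protects DLTs and the non-evaluability clause is limited to reasons unrelated to study drug. The ineligibility clause has no comparable safeguard.

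At stake is a level being called acceptable while the DLTs seen in treated patients reach a number that would have failed it had they all been counted.

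**Working it through.** The plan gives no target DLT rate and no operating characteristics for this rule, so there is no figure of its own to reproduce.

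**Inputs.** From the documents: 7 accrued, 6 counted, and two thresholds (unacceptable at 2 or more of 6; acceptable at no more than 2 of 6). Assumed: true DLT rate p from 10% to 40%, patients independent, all 7 evaluable.

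**Threshold of 2 or more (Sections 13.13.1 and 13.16, synopsis).** A level with 2 DLTs in 7 passes when exactly one of the first 6 and also the 7th has a DLT:

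P = [6 × p × (1 − p)^5] × p

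At p = 0.30: 6 × 0.30 × 0.16807 = 0.3025, and 0.3025 × 0.30 = 0.091.

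The chance of acceptance is P(X ≤ 1) = (1 − p)^n + n × p × (1 − p)^(n−1), with n = 6 or 7.

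| True DLT rate | 10% | 20% | 30% | 40% |
|---|---|---|---|---|
| 2 of 7 seen, level passes | 3.5% | 7.9% | 9.1% | 7.5% |
| Accepted, first 6 counted | 88.6% | 65.5% | 42.0% | 23.3% |
| Accepted, all 7 counted, limit still 2 | 85.0% | 57.7% | 32.9% | 15.9% |

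The first row is the difference between the other two, apart from rounding. Given exactly 2 DLTs among 7 exchangeable patients, the uncounted 7th is one of them with probability 2/7 = 28.6%.

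**Threshold of no more than 2 (Section 21.1.1).** Two DLTs among the 6 counted pass with nothing left out. The omission matters at 3 of 7:

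P = [15 × p² × (1 − p)^4] × p

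This gives 1.0%, 4.9%, 9.7% and 12.4% at 10%, 20%, 30% and 40%. At p = 1/3 it is 0.329 × 0.333 = 0.110, about 11%.

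**Later ineligibility.** Suppose 7 patients are dosed and 2 have DLTs, one of whom is later found ineligible. Removing that patient leaves 6 counted with 1 DLT, which passes under either threshold. No replacement is needed, so the rule that nobody is replaced once 2 or more have DLTs does not prevent it. With only 6 evaluable at the outset, removal leaves 1 of 5, and the final count depends on the replacement. The documents give no frequency for later ineligibility, so this route has no probability attached.

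**The case against.** The case for leaving the rule alone has real force.

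- **The 7th patient is a declared spare.** The first-6 rule is prespecified and depends on order, not outcome. It ignores a DLT-free 7th patient as well. If order is fixed independently of outcome, the first 6 estimate the DLT rate without bias. A reader might infer that the rule biases the estimated rate downward; the documents do not support that. What stands is narrower: under a fixed limit on the number of DLTs, a DLT-free 7th patient could not change the decision, while one with a DLT could.
- **Counting 7 against a limit of 2 is a stricter rule**, 2/7 (29%) in place of 2/6 (33%). The fall in acceptance from 42.0% to 32.9% at a 30% rate is the effect of that stricter rule and should not be read as an error rate. With no documented target, passing a level at 20% cannot be called a mistake.
- **There is a safety review.** The sponsor and investigators review each cohort before escalation, and escalation is permitted, not compelled. A DLT in the 7th patient would be visible. This is judgement, however; no rule requires an uncounted DLT to enter the decision.

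Two further inferences go too far. A reader might say that these patients count for efficacy but not for safety. Section 21.3 uses one primary population for both, and Section 21.5 summarises all adverse events. A reader might also take central pathology as a sure source of late ineligibility, because one slide is used "to confirm diagnosis and determine eligibility for further study". The next sentence of Section 21.7.1 assigns the remaining slides to MGMT and biomarker work, so the phrase may mean only that the tissue is suitable for testing.

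**Conclusion.** The point holds in limited form. Both routes are in the text: a DLT in a 7th evaluable patient is not counted, and a DLT in a treated patient later found ineligible is removed. The second is the clearer defect, since it departs from the protection given in the missed-dose rule.

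For the 7th patient the effect is 3.5% to 9.1% over assumed true rates of 10% to 40% under the 2-or-more threshold. Under the Section 21.1.1 threshold, the chance of 3 of 7 passing is 1.0% to 12.4%. These figures are conditional on all 7 being evaluable. The documents do not give that probability, so the unconditional effect is smaller.

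It would be too strong to say that the omission is why a level with two DLTs can be accepted. That is so only under the 2-or-more threshold; under Section 21.1.1 two counted DLTs already pass. The conflict between the thresholds is a separate and larger problem. No view is taken here on which is right.

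**What to change.** 1. Reconcile the acceptability threshold in Section 21.1.1 with that in Sections 13.13.1 and 13.16 and the synopsis.
2. In Section 21.1.1, add an exception to the ineligibility exclusion: a patient who received PLX3397 and had an observed DLT stays in the DLT count.
3. In Sections 21.1.1, 13.13.1 and 13.16 and the synopsis, have a DLT in any treated patient, including the 7th, enter the acceptability decision.
4. State how the reconciled threshold applies when 6 and when 7 patients are evaluable.

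These are wording changes and need no extra visits or longer observation. The statistical cost falls on tolerable levels. If the limit stays at 2 DLTs while 7 patients are counted, rejection rises from 11.4% to 15.0% at a true rate of 10%, and from 34.5% to 42.3% at 20%. It also makes the rule's strictness depend on how many patients are evaluable, which is why step 4 is needed.

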#### **21.1.2 Phase 2 Portion**

For Part 2 (Phase 2 portion), the primary objective is the comparison of median Progression Free Survival (PFS) to historical control. Secondary objectives include the evaluation of overall survival (OS), pharmacokinetics (PK), correlative imaging studies, safety, and the exploratory endpoint of pharmacodynamic (PD) effects of PLX3397.

### **21.2 Sample Size and Power**

For the primary endpoint of median PFS, based on a one-sided log rank test with a significance level of 0.1 and power of 80%, 22 events (death or progression) in approximately 31 patients would be required to detect a 50% relative hazard reduction in progression-free survival due to the addition of PLX3397 compared to the recent historical control median PFS of 5.5 months (RTOG 0525). Assuming a ~30% rate of non-evaluability, approximately 37 patients are planned to be enrolled in the Phase 2 portion of the study, which when combined with the 7 patients treated at that dose level in the Phase 1 portion of the study will yield approximately 44 patients.

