Statistical Considerations	For the primary endpoint of median PFS, based on a one-sided log rank test with a significance level of 0.1 and power of 80%, 22 events (death or progression) in approximately 31 patients would be required to detect a 50% relative hazard reduction in progression-free survival due to the addition of PLX3397 compared to the recent historical control median PFS of 5.5 months (RTOG 0525). Assuming a ~ 30% rate of non-evaluability, approximately 37 patients are planned to be enrolled in the Phase 2 portion of the study, which when combined with the 7 patients treated at that dose level in the Phase 1 portion of the study will yield approximately 44 patients.

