## 10.0 DESIGN

### 10.1 Description

This will be an open label, uncontrolled Phase 1b/2 trial in patients with newly diagnosed GBM who have recovered from complete or partial surgical resection. All patients will be treated with PLX3397 in addition to standard-of-care combination radiation therapy (RT) plus temozolomide (TMZ) followed by adjuvant TMZ. During Phase 1b dose escalation, two PLX3397 administration schedules, 7 days/week vs. 5 days/week (M-F) will be explored. During Phase 2, patients will be treated with the RP2D.

There are 4 sequential periods: 1-week PLX3397 monotherapy; 6-week PLX3397/RT/TMZ combination therapy; 4-week recovery; and, PLX3397/TMZ adjuvant therapy. PLX3397 will be administered twice daily either 7 days/week or 5 days/week (Monday through Friday) starting 1 week prior to the initiation of RT and will continue twice daily either 7 days/week or 5 days/week (Monday through Friday) during the 6-week course of RT.

Phase 1b PLX3397 dose and schedule cohorts are shown in [Table 2](#).

A detailed Trial Flow Chart is available in [Section 6.0](#), and procedures by study day are provided in [Section 13.0](#).

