#### **10.5 Duration of Study**

The duration of the Phase 1b portion of the study will depend on the number of cohorts required and the need for replacement patients. For the Phase 2 portion of the study, a recruitment rate of 1 patient per site per month is anticipated. The total duration of enrollment is expected to be approximately 18 months. The duration of follow-up will depend on the prolongation of the median PFS; the study is powered to detect a median PFS of approximately 8 months.

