#### 21.4 Efficacy Analysis

Response to treatment will be evaluated using the Response Assessment in Neuro-Oncology (RANO) criteria (Wen 2010). The response criteria are summarized in Attachment 3. All patients who are eligible for efficacy analyses will be evaluable for PFS, calculated for each subject as the number of days from the first day of treatment (C1D1) to the date of the first documented disease progression or date of death, whichever occurs first. The Kaplan-Meier method will be used to estimate the median PFS.

Statistical modeling will be used to match the experimental group to the RTOG 0525 historical group for expected prognosis based on both clinical and molecular factors, importantly the level of MGMT methylation in the tumor tissue.

For each subject with a response to therapy, duration of response will be calculated. The duration of response is defined as number of days from the date of initial response to the date of first documented disease progression or death, whichever occurs first. The Kaplan-Meier method will be used to estimate median duration of response. In the event no disease progression or death is documented prior to study termination, analysis cutoff, or the start of confounding anticancer therapy, PFS and duration of response will be censored at the date of last evaluable tumor assessments. The median duration will be compared to the historical control PFS of 5.5 months. The secondary endpoint of OS will be analyzed in a similar fashion.

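### The stated 22 events do not match a 50% hazard reduction at 80% power (about 7–10 events would do), and that effect conflicts with the 8-month target in section 10.5

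*Combined protocol and SAP*

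**What the plan says.** Section 21.2 sets the Phase 2 sample size with a one-sided log-rank test at 0.10 and 80% power. It requires "22 events (death or progression) in approximately 31 patients", and the effect is given as the number that "would be required to detect a 50% relative hazard reduction in progression-free survival due to the addition of PLX3397". The comparator is a historical median PFS of 5.5 months from RTOG 0525. The Statistical Considerations row of the synopsis repeats this: "22 events (death or progression) in approximately 31 patients would be required to detect a 50% relative hazard reduction".

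Section 10.5 describes the target differently: "the study is powered to detect a median PFS of approximately 8 months".

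On design, section 10.1 says "This will be an open label, uncontrolled Phase 1b/2 trial in patients with newly diagnosed GBM", so there is no concurrent control arm. Section 21.4 adds that "Statistical modeling will be used to match the experimental group to the RTOG 0525 historical group", and the PD Parameters row of the synopsis allows the 5.5-month benchmark to be adjusted for MGMT methylation status. No section says whether the log-rank test is one-sample or two-sample, which variance it uses, what survival distribution is assumed, or how large the historical group is.

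**The concern.** Hazard ratio, alpha, power and event count are tied together: once three are fixed, the fourth follows. Here all four are stated, and 22 events looks like far too many for a halving of the hazard against a fixed benchmark. A halved hazard also appears to imply a median well beyond 8 months.

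These figures are the operating characteristics of the Phase 2 primary analysis, and section 21.2 is the only sample-size justification in the body of the protocol. A reader of 21.2 would think the trial has only 80% power for a doubling of median PFS. A reader of 10.5 would take 80% power at 8 months as settled. A negative result would be interpreted differently under the two readings.

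**Working it through.** **Inputs.** One-sided alpha 0.10, power 80%, 22 events, hazard ratio (HR) 0.50 and historical median 5.5 months (21.2); target median about 8 months (10.5); single arm (10.1). z(0.90) = 1.2816 and z(0.80) = 0.8416, so (1.2816 + 0.8416)² = 4.508.

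**Medians, assuming exponential PFS.** HR 0.50 gives 5.5/0.50 = 11.0 months. A median of 8.0 months gives HR = 5.5/8.0 = 0.6875, a 31% reduction. A 50% longer median, 8.25 months, gives HR 0.667.

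**Reproducing the plan's figure at HR 0.50, fixed reference.** Events for 80% power:

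- Log-hazard form: d = 4.508 / ln(0.50)² = 4.508 / 0.4805 = 9.4.
- Two-variance one-sample log-rank: d = HR·(1.2816 + 0.8416·√HR)² / (1 − HR)² = 7.0.
- Exact exponential (gamma) test: 10.
- Single-variance form based on (O − E)/√O: d = 4.508 / (1/HR − 1)² = 4.508 / 1 = 4.5.

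None gives 22. A two-sided 0.10 test needs only 10 to 13 by the first three forms. A two-sample 1:1 log-rank needs 4 × 4.508 / 0.4805 = 37.5 events in total (Schoenfeld) or 4.508 × (1.5/0.5)² = 40.6 (Freedman); 22 events in total would give 63% power.

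**Events needed for 80% power at each target:**

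| Form | HR 0.50 (11.0 mo) | HR 0.667 (8.25 mo) | HR 0.6875 (8.0 mo) |
|---|---|---|---|
| Log-hazard | 9.4 | 27.4 | 32.1 |
| One-sample log-rank, two-variance | 7.0 | 23.3 | 27.6 |
| Exact | 10 | 27 | 32 |
| (O − E)/√O, single variance | 4.5 | 18.0 | 21.8 |

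**Power delivered by 22 events:**

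| Form | HR 0.50 | HR 0.667 | HR 0.6875 |
|---|---|---|---|
| Log-hazard | 97.6% | 73.2% | 68.3% |
| One-sample log-rank, two-variance | 99.8% | 78.1% | 72.1% |
| Exact | 96.9% | 74.2% | 69.5% |
| (O − E)/√O, nominal | 99.97% | 85.6% | 80.2% |

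The last row is the formula value. Evaluated exactly with 22 events fixed, the (O − E)/√O statistic rejects when E exceeds 22 + 1.2816·√22 = 28.01. Its size is 10.6% and its power 97.1%, 75.1% and 70.5%, so the 80.2% is nominal only.

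**Effect that 22 events detect with 80% power.** HR 0.636 to 0.688, a reduction of 31–36%. The corresponding medians are 7.99 months ((O − E)/√O), 8.34 (one-sample log-rank), 8.62 (exact) and 8.65 (log-hazard).

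**Simulation check.** A one-sample log-rank with variance E, 31 patients, 18-month uniform accrual and analysis at the 22nd event gave 96.3% power at HR 0.50 and 65% at 8.0 months, with size 7.7%. At HR 0.50, 7 events gave 66% and 10 gave 78%, so the upper end of the 7–10 range is the more realistic.

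**Patient numbers.** 31/0.7 = 44.3, and 37 + 7 = 44. These agree.

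**The case against.** There are four serious counter-arguments.

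- **The comparison may not be to a fixed value.** Section 21.4 plans matching to the RTOG 0525 group. Half of the 1:1 two-sample total at HR 0.50 is 18.8 (Schoenfeld) or 20.3 (Freedman) events per arm, close to 22. But the trial has no 1:1 control arm, and 21.2 names a single historical median. If a historical group contributed 50 to 500 events (an assumption, as its size is not given), the trial would need about 9.6 to 11.5 events at HR 0.50. Needing 22 would take a historical group with only about 16 events.
- **The 11-month figure assumes exponential PFS.** Under proportional hazards with Weibull PFS, HR 0.50 gives 9.8 months at shape 1.2, 8.7 at shape 1.5 and 8.0 at shape 1.85. This could remove the conflict with 10.5, but the documents state no such shape. It leaves the event-count mismatch untouched, because the fixed-reference requirement depends on the hazard ratio.
- **The likely source of the error is a guess.** At 8.25 months the one-sample log-rank needs 23.3 events, so a 50% increase in median could also explain the figure of 50%. This stands, and is why the sponsor's own calculation has to be checked first.
- **The error is conservative for HR 0.50.** More events than needed do not inflate the type I error. That is true, but if 8 months is the real target, the stated 80% is too favourable under most forms.

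**Conclusion.** The inconsistency is real. In the single-arm comparison described, 22 events, one-sided 0.10, 80% power and HR 0.50 cannot all hold: about 7 to 10 events would suffice, and 22 give about 97% power or more by formula or exact test (96% in simulation). This does not depend on the exponential assumption for the medians.

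The conflict with section 10.5 does depend on it: 11 months against about 8 months. The event count fits the 8-month region much better than the 11-month one, so the 50% hazard-reduction wording is the most probable error, but this is inference. At exactly 8.0 months, power is 68–72% by the log-hazard, exact and two-variance log-rank forms, and 80.2% only nominally by the (O − E)/√O form. Because the test form is unstated, a reader cannot tell which power was intended.

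**What to change.** The sponsor should retrieve its original calculation, then give the same statement in 21.2, 10.5 and the Statistical Considerations row of the synopsis:

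- one target, as a hazard ratio with its median and the survival assumption linking them;
- the test (one-sample, or against a matched historical group of stated size) and its variance form;
- the event count, and the power it gives under that test.

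If about 8 months was meant, 21.2 and the synopsis could describe an increase in median PFS from 5.5 to about 8 months (HR about 0.69, a 31% hazard reduction), with the power of 22 events under the named test, about 68–72% by the usual forms. If HR 0.50 was meant, section 10.5 and either the stated power or the event count need correcting.

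The cost is text edits after one check, with planned enrolment left at 44. The downside is that the stated power at 8 months may become less favourable. Insisting on 80% at 8.0 months under the usual forms would be a larger change: it needs about 28 to 32 events (27.6 to 32.1), against 31 evaluable patients.
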